15.8. Appendix 8: Values of Potential Clinical Importance

15.8.1. Laboratory Values

Haematology				
Laboratory Parameter	Units	Category	Clinical Concern Range	
			Low Flag (< x)	High Flag (> x)
Haematocrit	Ratio of 1	Male		0.54
		Δ from BL	↓ 0.075	
Haemoglobin	g/L	Male		180
		Δ from BL	↓ 25	
Lymphocytes	x10 ⁹ /L		0.8	
Neutrophil Count	x10 ⁹ /L		1.5	
Eosinophil Count	x10 ⁹ /L			1
Platelet Count	x10 ⁹ /L		100	550
While Blood Cell Count (WBC)	x10 ⁹ /L		3	20

Clinical Chemistry				
Laboratory Parameter	Units	Category	Clinical Concern Range	
			Low Flag (< x)	High Flag (> x)
Blood urea nitrogen	mmol/L			10.5
Calcium	mmol/L		2	2.75
Creatinine	μmol/L	Δ from BL		↑ 26
eGFR	ml/min/1.73m ²		60	
Glucose	mmol/L		3	9
Potassium	mmol/L		3	5.5
Sodium	mmol/L		130	150
Total Protein	g/L		50	85

Liver Function				
Test Analyte	Units	Category	Clinical Concern Range	
ALT/SGPT	U/L	High	≥ 2 x ULN	
AST/SGOT	U/L	High	≥ 2 x ULN	
AlkPhos	U/L	High	≥ 2 x ULN	
T Bilirubin	μmol/L	High	≥ 1.5 x ULN	
T. Bilirubin + ALT	μmol/L U/L	High	≥ 1.5 x ULN T. Bilirubin + ≥ 2 x ULN ALT	

15.8.2. ECG

ECG Parameter	Units	Clinical Concern Range	
		Lower	Upper
Absolute			
Absolute QTc Interval	msec		> 450
Absolute PR Interval	msec	< 110	> 220
Absolute QRS Interval	msec	< 75	> 110
Change from Baseline			
Increase from Baseline QTc	msec		> 60

15.8.3. Vital Signs

Vital Sign Parameter (Absolute)	Units	Clinical Concern Range	
		Lower	Upper
Systolic Blood Pressure	mmHg	< 85	> 160
Diastolic Blood Pressure	mmHg	< 45	> 100
Heart Rate	bpm	< 40	> 110
Temperature	°C	<35	≥37.5

15.8.4. Urinalysis

Urinalysis			
Test Analyte	Units	Category	Clinical Concern Range
Bilirubin		High	>1+
Glucose		High	>1+
Ketone		High	>2+
Leukocytes (dipstick)		High	>1+
Nitrite		High	Positive
Occult blood (dipstick)		High	>1+
pH		Low	<4.6
		High	>8
Protein		High	>1+
RBC (microscopy)	cells/hpf	High	>3
Specific gravity		Low	<1.001
		High	>1.035
Urobilinogen	mg/dL	High	>1
WBC (microscopy)	cells/hpf	High	>5

15.9. Appendix 9: Population Pharmacokinetic (PopPK) Analyses

15.9.1. Population Pharmacokinetic (PopPK) Dataset Specification

PopPK dataset specification will be provided as a separate document.

15.9.2. Population Pharmacokinetic (PopPK) Methodology

An exploratory graphical analysis of the drug plasma concentration-time data will be performed by generating the plots as presented in [Appendix 12: List of Data Displays](#).

A previous PopPK model developed from the first time in human study 200630 (GSK Document Number 2017N352860_00), incorporating linear and non-linear (target mediated drug disposition (TMDD), Michaelis-Menten) elimination pathways, will be used to fit the drug plasma concentration-time data. The model will be updated accordingly to describe the absorption profiles after SC doses of GSK2831781. For this update it will be assumed that the distribution and elimination of GSK2831781 will be the same regardless of the route of administration (IV or SC).

The appropriateness of the updated model will be assessed by the objective function value (OFV), successful convergence, covariance estimation, shrinkage, parameter uncertainty, standard Goodness-of-Fit (GoF) and simulation-based diagnostic plots e.g. Visual Predictive Check (VPC).

The GoF plots may include, but are not limited to:

- Population and individual predictions versus observations
- Conditional weighted residuals versus population predictions and time

If a VPC is done, this will be based on 1000 simulations with the model and the design structure of the observed data (i.e. dose level and time, time of PK sampling and individual values of model covariates, if any). The median and the 10th and 90th will be compared to the observed data. Stratification by dose level and administration route of GSK2831781 or geographic ancestry will be used.

The individual PK parameters will be computed from the PopPK model and will be summarised by treatment group and geographic ancestry.

15.10. Appendix 10: Pharmacokinetic / Pharmacodynamic Analyses

15.10.1. Pharmacokinetic / Pharmacodynamic Dataset Specification

PK/PD dataset specification will be provided as a separate document.

15.10.2. Pharmacokinetic / Pharmacodynamic Methodology

An exploratory graphical analysis of the drug effect on LAG3⁺ cell depletion, sLAG3 concentrations and regulatory T cells count will be performed by generating the PD plots as presented in [Appendix 12: List of Data Displays](#).

A previous indirect response model developed from all available cell depletion data from the first-time in human study 200630 (GSK Document Number 2017N352860_00) will be fitted to the current PD data using the nonlinear mixed effects modelling software NONMEM. Data relative to CD4⁺CD45RA⁻1B4⁺ cell count will be used to model T cell depletion.

The appropriateness of the PopPK/PD model will be assessed by the OFV, successful convergence, covariance estimation, shrinkage, parameter uncertainty, standard GoF and simulation-based diagnostic plots e.g. VPC.

The GoF plots may include, but are not limited to:

- Population and individual predictions versus observations
- Conditional weighted residuals versus population predictions and time

If a VPC is done, this will be based on 1000 simulations with the model and the design structure of the observed data (i.e. dose level and time, time of PD sampling and individual values of model covariates, if any). The median and the 10th and 90th will be compared to the observed data. Stratification by dose level and administration route of GSK2831781 or geographic ancestry will be used.

15.11. Appendix 11: Abbreviations & Trade Marks**15.11.1. Abbreviations**

Abbreviation	Description
ADA	Anti-drug antibody
AE	Adverse Event
ALT	Alanine aminotransaminase
ANOVA	Analysis of variance
AST	Aspartate Aminotransferase
AUC(0-t)	Area under the plasma concentration-time curve from time zero (pre-dose) to last time of quantifiable concentration
A&R	Analysis and Reporting
BUN	Blood Urea Nitrogen
CI	Confidence Interval
C _{max}	Maximum observed plasma concentration
CMV	Cytomegalovirus
CPEM	Clinical Pharmacology and Experimental Medicine
CPMS	Clinical Pharmacology Modelling & Simulation
CRF	Case Record Form
CSV	Comma-separated values
CV _b / CV _w	Coefficient of Variation (Between) / Coefficient of Variation (Within)
DBF	Database Freeze
DBR	Database Release
DP	Decimal Places
EBV	Epstein-Barr Virus
ECG	Electrocardiogram
eCRF	Electronic Case Record Form
eGFR	Estimated Glomerular Filtration Rate
EMA	European Medicines Agency
F	Bioavailability
FDA	Food and Drug Administration
FDAAA	Food and Drug Administration Clinical Results Disclosure Requirements
GCDO	Global Clinical & Data Operations
GCSD	Global Clinical Sciences & Delivery
GoF	Goodness-of-Fit
GSK	GlaxoSmithKline
HARP	Harmonized Analysis and Reporting Process
HbcAb	Hepatitis B core antibody
HbsAg	Hepatitis B surface antigen
HCV	Hepatitis C virus
HIV	Human Immunodeficiency Virus
IA	Interim Analysis
ICH	International Conference on Harmonization
IDSL	Integrated Data Standards Library
INR	International normalized ratio

Abbreviation	Description
IP	Investigational Product
IV	Intravenous
LAG3	Lymphocyte Activation Gene-3
MCH	Mean Corpuscular Hemoglobin
MCV	Mean Corpuscular Volume
NQ	Non-quantifiable
OFV	Objective Function Value
PCI	Potential Clinical Importance
PD	Pharmacodynamic
PDMP	Protocol Deviation Management Plan
PK	Pharmacokinetic
PKPD	Pharmacokinetic / Pharmacodynamic
PopPK	Population PK
QC	Quality Control
QTcF	Frederica's QT Interval Corrected for Heart Rate
QTcB	Bazett's QT Interval Corrected for Heart Rate
RAP	Reporting & Analysis Plan
RAMOS	Randomization & Medication Ordering System
RBC	Red Blood Cell
RC	(Interim) Review Committee
RTF	Rich Text Format
SAC	Statistical Analysis Complete
SAE	Serious Adverse Event
SC	Subcutaneous
SD	Standard Deviation
SGOT	Serum Glutamic-Oxaloacetic Transaminase
SGPT	Serum Glutamic-Pyruvic Transaminase
sLAG3	Soluble LAG3
SMG	Safety and Medical Governance
SoA	Schedule of Activities
SOP	Standard Operation Procedure
TA	Therapeutic Area
TB	Tuberculosis
TLF	Tables, Listings & Figures
tmax	Time of occurrence of Cmax
TMDD	Target Mediated Drug Disposition
ULN	Upper limit of normal
VPC	Visual Predictive Check
VZV	Varicella zoster virus
WBC	White Blood Cell
WNL	Windows Non-Linear

15.11.2. Trademarks

Trademarks of the GlaxoSmithKline Group of Companies
None

Trademarks not owned by the GlaxoSmithKline Group of Companies
NONMEM
SAS
WinNonlin

15.12. Appendix 12: List of Data Displays

15.12.1. Data Display Numbering

The following numbering will be applied for RAP generated displays:

Section	Tables	Figures
Study Population	1.1 to 1.20	-
Safety	2.1 to 2.34	2.1 to 2.2
Pharmacokinetic	3.1 to 3.8	3.1 to 3.4
Population Pharmacokinetic (PopPK)	4.1 to 4.x*	4.1 to 4.x*
Pharmacodynamic	5.1 to 5.7	5.1 to 5.10
Pharmacokinetic / Pharmacodynamic	6.1 to 6.x*	6.1 to 6.x*
Section	Listings	
ICH Listings	1 to 66	
Other Listings	67 to x*	

* PopPK and PK/PD displays will be generated by CPMS as needed; the number of displays is not pre-defined.

15.12.2. Mock Example Shell Referencing

Non IDSL specifications will be referenced as indicated and if required example mock-up displays provided in [Appendix 13](#): Example Mock Shells for Data Displays.

Section	Figure	Table	Listing
Study Population	-	-	POP_Ln
Safety	SAFE_Fn	-	SAFE_Ln
Pharmacokinetic	-	PK_Tn	-
Population Pharmacokinetic (PopPK)	-	-	-
Pharmacodynamic	PD_Fn	-	PD_Ln
Pharmacokinetic / Pharmacodynamic	-	-	-

NOTES:

- Non-Standard displays are indicated in the 'IDSL / Example Shell' or 'Programming Notes' column as '[Non-Standard] + Reference.'

15.12.3. Deliverables

Delivery	Description
IA	Interim Analysis Statistical Analysis Complete
SAC	Final Statistical Analysis Complete

15.12.4. Study Population Tables

Part A

Study Population Tables (Part A)					
No.	Population	IDSL / Example Shell	Title	Programming Notes	Deliverable [Priority]
Subject Disposition					
1.1.	Safety	ES1	Part A: Summary of Subject Disposition for the Subject Conclusion Record	Add footnote: Note: "Subjects" is used to refer to "Participants" in all data displays to reflect GSK display standards. By treatment and geographic ancestry.	IA SAC
1.2.	Screened	ES6	Part A: Summary of Screening Status and Reasons for Screen Failure		SAC
Protocol Deviation					
1.3.	Safety	DV1	Part A: Summary of Important Protocol Deviations	By treatment and geographic ancestry. Include Total column.	SAC
Population Analysed					
1.4.	Screened	SP1	Part A: Summary of Study Populations	By treatment and geographic ancestry.	IA SAC
Demographic and Baseline Characteristics					
1.5.	Safety	DM1	Part A: Summary of Demographic Characteristics	By treatment and geographic ancestry.	IA SAC
1.6.	Safety	DM5	Part A: Summary of Race and Racial Combinations	Only include race detail categories with >0 subjects. By treatment.	SAC
1.7.	Randomized	DM11	Part A: Summary of Age Ranges	By treatment and geographic ancestry.	SAC
Medical Conditions					

Study Population Tables (Part A)					
No.	Population	IDSL / Example Shell	Title	Programming Notes	Deliverable [Priority]
1.8.	Safety	MH1	Part A: Summary of Past Medical Conditions	By treatment and geographic ancestry.	SAC
1.9.	Safety	MH1	Part A: Summary of Current Medical Conditions	By treatment and geographic ancestry.	SAC
Exposure and Treatment Compliance					
1.10.	Safety	EX1	Part A: Summary of Exposure to Study Treatment	By treatment and geographic ancestry.	SAC

Part B

Study Population Tables (Part B)					
No.	Population	IDSL / Example Shell	Title	Programming Notes	Deliverable [Priority]
Subject Disposition					
1.11.	Safety	ES1	Part B: Summary of Subject Disposition for the Subject Conclusion Record	By treatment.	SAC
1.12.	Screened	ES6	Part B: Summary of Screening Status and Reasons for Screen Failure		SAC
Protocol Deviation					
1.13.	Safety	DV1	Part B: Summary of Important Protocol Deviations	By treatment. Include Total column.	SAC
Population Analysed					
1.14.	Screened	SP1	Part B: Summary of Study Populations	By treatment.	SAC
Demographic and Baseline Characteristics					
1.15.	Safety	DM1	Part B: Summary of Demographic Characteristics	By treatment.	SAC

Study Population Tables (Part B)					
No.	Population	IDSL / Example Shell	Title	Programming Notes	Deliverable [Priority]
1.16.	Safety	DM5	Part B: Summary of Race and Racial Combinations	Only include race detail categories with >0 subjects. By treatment.	SAC
1.17.	Randomized	DM11	Part B: Summary of Age Ranges	By treatment.	SAC
Medical Conditions					
1.18.	Safety	MH1	Part B: Summary of Past Medical Conditions	By treatment.	SAC
1.19.	Safety	MH1	Part B: Summary of Current Medical Conditions	By treatment.	SAC
Exposure and Treatment Compliance					
1.20.	Safety	EX1	Part B: Summary of Exposure to Study Treatment	By treatment.	SAC

15.12.5. Safety Tables**Part A**

Safety Tables (Part A)					
No.	Population	IDSL / Example Shell	Title	Programming Notes	Deliverable [Priority]
Adverse Events (AEs)					
2.1.	Safety	AE1	Part A: Summary of All Adverse Events by System Organ Class and Preferred Term	IA: By geographic ancestry. SAC: By treatment and geographic ancestry.	IA SAC
2.2.	Safety	AE3	Part A: Summary of Drug-Related Adverse Events	IA: By geographic ancestry. SAC: By treatment and geographic ancestry.	IA SAC
2.3.	Safety	AE3	Part A: Summary of Non-Serious Drug-Related Adverse Events by Overall Frequency	By treatment and geographic ancestry.	SAC
2.4.	Safety	AE5A	Part A: Summary of All Adverse Events by Maximum Intensity by System Organ Class and Preferred Term	Page by treatment and geographic ancestry.	SAC
2.5.	Safety	AE5A	Part A: Summary of Drug-Related Adverse Events by Maximum Intensity by System Organ Class and Preferred Term	Page by treatment and geographic ancestry.	SAC
Serious and Other Significant Adverse Events					
2.6.	Safety	AE16	Part A: Summary of Serious Adverse Events by System Organ Class and Preferred Term (Number of Subjects and Occurrences)	IA: By geographic ancestry. SAC: By treatment and geographic ancestry.	IA SAC
2.7.	Safety	AE3	Part A: Summary of Serious Drug-Related Adverse Events by Overall Frequency	IA: By geographic ancestry. SAC: By treatment and geographic ancestry.	IA SAC
2.8.	Safety	AE3	Part A: Summary of Adverse Events Leading to Permanent Discontinuation of Study Treatment or Withdrawal from Study	By treatment and geographic ancestry.	SAC

Safety Tables (Part A)					
No.	Population	IDSL / Example Shell	Title	Programming Notes	Deliverable [Priority]
Laboratory: Chemistry					
2.9.	Safety	LB1	Part A: Summary of Chemistry Changes from Baseline	By treatment and geographic ancestry.	SAC
Laboratory: Haematology					
2.10.	Safety	LB1	Part A: Summary of Haematology Changes from Baseline	By treatment and geographic ancestry. IA: Only include the following parameters: Neutrophils, Lymphocytes.	IA SAC
Laboratory: Urinalysis					
2.11.	Safety	LB1	Part A: Summary of Urine Concentration Changes from Baseline	By treatment and geographic ancestry.	SAC
Laboratory: Hepatobiliary (Liver)					
2.12.	Safety	LIVER1	Part A: Summary of Liver Monitoring/Stopping Event Reporting	By treatment and geographic ancestry.	IA SAC
2.13.	Safety	LIVER10	Part A: Summary of Hepatobiliary Laboratory Abnormalities	By treatment and geographic ancestry.	SAC
ECG					
2.14.	Safety	EG1	Part A: Summary of ECG Findings	By treatment and geographic ancestry.	SAC
2.15.	Safety	EG10	Part A: Summary of Maximum QTc Values Post-Baseline Relative to Baseline by Category	By treatment and geographic ancestry.	SAC
2.16.	Safety	EG2	Part A: Summary of Change from Baseline in ECG Values by Visit	By treatment and geographic ancestry.	SAC
Vital Signs					
2.17.	Safety	VS1	Part A: Summary of Change from Baseline in Vital Signs	By treatment and geographic ancestry.	SAC

Part B

Safety Tables (Part B)					
No.	Population	IDSL / Example Shell	Title	Programming Notes	Deliverable [Priority]
Adverse Events (AEs)					
2.18.	Safety	AE1	Part B: Summary of All Adverse Events by System Organ Class and Preferred Term	By treatment.	SAC
2.19.	Safety	AE3	Part B: Summary of Drug-Related Adverse Events	By treatment.	SAC
2.20.	Safety	AE3	Part B: Summary of Non-Serious Drug-Related Adverse Events by Overall Frequency	By treatment.	SAC
2.21.	Safety	AE5A	Part B: Summary of All Adverse Events by Maximum Intensity by System Organ Class and Preferred Term	Page by treatment.	SAC
2.22.	Safety	AE5A	Part B: Summary of Drug-Related Adverse Events by Maximum Intensity by System Organ Class and Preferred Term	Page by treatment.	SAC
Serious and Other Significant Adverse Events					
2.23.	Safety	AE16	Part B: Summary of Serious Adverse Events by System Organ Class and Preferred Term (Number of Subjects and Occurrences)	By treatment.	SAC
2.24.	Safety	AE3	Part B: Summary of Serious Drug-Related Adverse Events by Overall Frequency	By treatment.	SAC
2.25.	Safety	AE3	Part B: Summary of Adverse Events Leading to Permanent Discontinuation of Study Treatment or Withdrawal from Study	By treatment.	SAC
Laboratory: Chemistry					
2.26.	Safety	LB1	Part B: Summary of Chemistry Changes from Baseline	By treatment.	SAC
Laboratory: Haematology					
2.27.	Safety	LB1	Part B: Summary of Haematology Changes from Baseline	By treatment.	SAC

Safety Tables (Part B)					
No.	Population	IDSL / Example Shell	Title	Programming Notes	Deliverable [Priority]
Laboratory: Urinalysis					
2.28.	Safety	LB1	Part B: Summary of Urine Concentration Changes from Baseline	By treatment.	SAC
Laboratory: Hepatobiliary (Liver)					
2.29.	Safety	LIVER1	Part B: Summary of Liver Monitoring/Stopping Event Reporting	By treatment.	SAC
2.30.	Safety	LIVER10	Part B: Summary of Hepatobiliary Laboratory Abnormalities	By treatment.	SAC
ECG					
2.31.	Safety	EG1	Part B: Summary of ECG Findings	By treatment.	SAC
2.32.	Safety	EG10	Part B: Summary of Maximum QTc Values Post-Baseline Relative to Baseline by Category	By treatment.	SAC
2.33.	Safety	EG2	Part B: Summary of Change from Baseline in ECG Values by Visit	By treatment.	SAC
Vital Signs					
2.34.	Safety	VS1	Part B: Summary of Change from Baseline in Vital Signs	By treatment.	SAC

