5.6. Placebo control

This study includes placebo arms to allow for a valid evaluation of AEs attributable to treatment versus those independent of treatment.

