10.2. Sample Size Determination

10.2.1. Part A

There will be a minimum of 8 Japanese and 8 Caucasian participants in Part A. The participants in each ethnicity stratum will be randomised 6:2 to GSK2831781 (450 mg) or placebo.

If 0/6 of a particular safety event is observed among the GSK2831781 participants of an ethnicity stratum, then the upper limit of the exact 95% Confidence Interval indicates that a true incidence rate of 41.0% could not be ruled out. Using a Bayesian approach to determine the credible interval around an observed safety event, we will assume a flat Beta (1,1) prior. If in an ethnicity stratum we were to observe 1 safety event out of the 6 participants who received GSK2831781, then the posterior distribution would be Beta (2,6). In that case there is a 95% certainty that the true probability of the safety event lies between 0.04 and 0.58.

The following between-subject coefficients of variation (CV_b) for the geometric means of PK parameters were observed in the FTIH study 200630 following GSK2831781 IV administration:

| Study 200630 Volunteer type | Treatment group | CV_b (%) | |
|--------------------------------|-----------------|------------|------|
| | | AUC (0-t) | Cmax |
| Healthy volunteer | 0.0075 mg/kg | 32.0 | 19.1 |
| Healthy volunteer | 0.04 mg/kg | 27.3 | 25.6 |
| Healthy volunteer | 0.15 mg/kg | 36.8 | 18.3 |
| Psoriasis patient | 0.5 mg/kg | 34.2 | 23.5 |
| Psoriasis patient | 1.5 mg/kg | 13.8 | 15.5 |
| Psoriasis patient | 5 mg/kg | 24.2 | 22.2 |

The 5 mg/kg dose corresponds to an average of 472 mg; therefore, the corresponding CV_b %'s are a good approximation for 450 mg.

Assuming a sample size of 6, it is estimated that the lower and upper bounds of the 90% confidence interval for the geometric means of area under the curve (AUC) and Cmax will be within approximately 21.7% and 19.8% of the point estimate respectively.

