11.1.5. Committees Structure

Safety Review Team (SRT)

In line with routine pharmacovigilance, an internal GSK SRT, which will include a limited number of 207823 study team members, will review blinded safety data, including clinical laboratory parameters and adverse events, at appropriate intervals during the period of study conduct. The SRT charter outlines the roles and responsibilities in more detail.

Data Review Committee (DRC)

During an Interim Analysis unblinded study data may be reviewed by the DRC, and decisions made based on the outlined criteria included in the DRC charter. The DRC will be composed of a limited number of people, who may be members of the 207823 study

team, including the statistician, a senior safety representative, lead physician and the pharmacokineticist. No members of the study team involved in the direct day-to-day conduct of the study or in the acquisition of data will take part in the DRC.

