3. PLANNED ANALYSES

3.1. Interim Analyses

An interim analysis for Part A will be performed once at least 8 participants in each stratum have completed their Day 8 visit, and at least 6 participants in each stratum have completed their Day 29 visit, where Safety, PK and PD data will be reviewed. The interim analysis will be utilised to determine if Japanese participants can be recruited into the Phase 2 study (204869) under the existing dosing strategy.

An Interim Data Review Committee (DRC) will be utilised in this study to review the interim analysis data. The DRC will be composed of a limited number of people, who may be members of the 207823 study team, including the statistician, a senior safety representative, lead physician and the pharmacokineticist. A DRC Charter will contain the details regarding the DRC, including membership, decision rules for the interim, and required data integrity and data quality control.

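### The four interim AE and SAE summary tables pool active and placebo within ancestry, although the other interim outcome summaries keep treatment

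*SAP*

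**What the plan says.** SAP 15.12.5 lists four Part A adverse event summaries as deliverables at both the interim (IA) and the final analysis (SAC): all AEs (Table 2.1), drug-related AEs (2.2), SAEs (2.6) and serious drug-related AEs (2.7). All four carry the same note: "IA: By geographic ancestry. SAC: By treatment and geographic ancestry".

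SAP 3.1 gives the purpose of the interim: "The interim analysis will be utilised to determine if Japanese participants can be recruited into the Phase 2 study (204869) under the existing dosing strategy". It takes place "once at least 8 participants in each stratum have completed their Day 8 visit", with at least 6 per stratum at Day 29. Protocol 10.2.1 gives the allocation: "The participants in each ethnicity stratum will be randomised 6:2 to GSK2831781 (450 mg) or placebo". Protocol 5.6 gives the reason for the control: "This study includes placebo arms to allow for a valid evaluation of AEs attributable to treatment versus those independent of treatment".

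Other displays in the same interim package keep treatment:

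- Haematology, Table 2.10: "By treatment and geographic ancestry. IA: Only include the following parameters: Neutrophils, Lymphocytes". Figures 2.1 and 2.2 follow the same split.
- Liver monitoring and stopping events (Table 2.12).
- PK (Tables 3.1 to 3.3, Figures 3.1 and 3.2).
- LAG3+ T cells and sLAG3 (Tables 5.1 and 5.2, Figures 5.1 to 5.4).
- Disposition, populations and demographics (Tables 1.1, 1.4 and 1.5).

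Listing 15, of all Part A adverse events, is also an interim deliverable. It has no note on whether treatment is shown.

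On access, Protocol 11.1.5 says "During an Interim Analysis unblinded study data may be reviewed by the DRC". It keeps staff in day-to-day conduct off the committee, and Protocol 10.5 excludes personnel in direct contact with sites. Protocol 7.4 allows members to be unblinded when individual data need review.

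**The concern.** Safety and tolerability is the primary objective, and placebo is in the design so that adverse events can be attributed. The interim is where a decision about Japanese participants is taken, yet its AE summaries are the outcome tables from which treatment has been removed. The SAP gives no reason.

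These tables carry much of the interim safety evidence. Chemistry, ECG and vital-sign summaries are produced only at the final analysis. Apart from AEs, the interim safety outcome summaries are neutrophils, lymphocytes and liver events.

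A pooled column mixes two rates. It can understate an effect confined to active drug, and an event in a placebo recipient counts towards an apparent difference between ancestry groups. A committee reading only these four tables could not tell these cases apart.

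**Working it through.** **Inputs.** Six active and two placebo per stratum (Protocol 10.2.1); at least eight per stratum at the interim (SAP 3.1); flat Beta(1,1) prior for safety rates (Protocol 10.2). The event counts and rates below are illustrative assumptions.

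**1. The plan's own figure.** Protocol 10.2.1 justifies the stratum size on participants who received drug: 1 event in 6 gives a posterior of Beta(2,6) and a 95% credible interval of 0.04 to 0.58. Recomputed quantiles are 0.037 and 0.579, so the figure reproduces. Its denominator is the 6 active participants, which the pooled tables do not show.

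**2. What a pooled count can hide.** A full interim column shows (x + y)/8, where x of 6 active and y of 2 placebo participants are affected. For a pooled 3/8 (37.5%, credible interval 0.14 to 0.70):

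| Active | Placebo | Active rate (95% credible interval) | Active minus placebo |
|---|---|---|---|
| 3/6 | 0/2 | 50% (0.18 to 0.82) | +50 points |
| 2/6 | 1/2 | 33% (0.10 to 0.71) | -17 points |
| 1/6 | 2/2 | 17% (0.04 to 0.58) | -83 points |

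The interim table prints the same entry in all three cases.

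**3. Dilution of the rate.** Pooled rate = (6 × active rate + 2 × placebo rate)/8. With 50% on active and 0% on placebo it is (6 × 0.50)/8 = 37.5%. With 30% and 0% it is 22.5%.

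**4. Dilution of the ancestry comparison.** Pooled difference = 0.75 × (difference on active) + 0.25 × (difference on placebo). If placebo rates are equal, the second term is zero and 75% of the active difference remains. With 3/6 Japanese and 1/6 Caucasian on active, 33 points reads as 0.75 × 33.3 = 25 points.

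**5. Chance placebo events.** If events are unrelated to treatment, a single affected participant is on placebo with probability 2/8 = 25%. With two affected of eight, at least one is on placebo with probability 1 - C(6,2)/C(8,2) = 1 - 15/28 = 46%.

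**6. How much the split would add.** Little precision. The credible interval for 0/2 on placebo is 0.01 to 0.71, and 3/6 v 0/2 gives a two-sided Fisher p of 0.46.

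**The case against.** The strongest reply has five parts.

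- **The committee has other routes to the information.** Listing 15 gives it AE-level data, and Protocol 7.4 lets it unblind where individual data need review. This stands, and it limits the point. A reader might infer that the placebo control is thrown away at the decision point. The documents do not support that: treatment is dropped from four summary tables, while neutropenia, the first risk in Protocol 3.3.1, keeps its comparison by arm. Listing 15 does not settle the matter, though. If it shows treatment, pooling the tables protects little. If it does not, no planned interim AE display is specified by arm.
- **Pooling may protect the blind.** Follow-up to Day 112 can still be running, and a preferred term reported once, shown by arm beside a listing, could reveal one person's treatment. The interim PK and PD individual plots suppress subject IDs, which fits this motive. It is possible but not stated, and it does not adequately explain the exception: liver events are tabulated by arm, and Figure 2.1 plots individual haematology by treatment with no instruction to suppress IDs.
- **Placebo recipients in the drug-related tables are not a fault of pooling.** Causality is assigned by a blinded investigator, so the same happens in the final tables. This stands; splitting the columns only makes it visible.
- **No changed decision has been shown.** With equal placebo rates, pooling shrinks the ancestry difference and does not reverse it. Chance events among active participants can also look like an ethnic difference. This stands.
- **Other safeguards exist.** Protocol 8.2 provides for dosing to halt or for safety team review, and Protocol 10.5 allows a further Day 112 interim. They are separate from how the interim tables should be read.

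**Conclusion.** The point holds for the four AE and SAE summary tables and no further. At the interim that informs Japanese entry to study 204869, they give neither the active-only rate on which the stratum size was justified nor the active-placebo contrast for which placebo was included. In a full column, 25% of participants are on placebo. A Japanese-Caucasian difference on active drug is reduced to 75% of its size, assuming 6:2 in both strata and equal placebo rates.

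The documents do not show that the committee would be unable to attribute events, or that its decision would change. The loss is of attribution and of the right denominator; two placebo participants per stratum are weak evidence under any layout. It is worth correcting because the layout departs from the rest of the interim package without a stated reason. Confidence is moderate: the DRC Charter, which holds the decision rules, and the display specifications are not available and may add displays by arm.

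**What to change.** In SAP 15.12.5, change the interim instruction on Tables 2.1, 2.2, 2.6 and 2.7 to the layout already specified for the final analysis, treatment by geographic ancestry, and restrict these tables to the DRC package. Keep subject IDs out of any interim AE display read beside them, including Listing 15, and state whether that listing shows treatment. If the sponsor prefers to keep the pooled layout, the SAP should say why and how AE attribution will be judged at the interim.

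The cost is four programming notes and a line on Listing 15. The final-analysis layout exists, and no new data or method is needed. The downside is that cells of 6 and 2 could reveal an individual's treatment to committee members, but they already see laboratory, liver, PK and PD data by arm and are kept apart from sites and day-to-day conduct.
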